#### Overview of analysis methods for efficacy variables Table 1-7

Variable(s)	Summary statistics for binary/ categorical data	Risk Difference	Logistic regression	Summary statistics for continuous data	Analysis of Co- variance	Time to event data analysis
PASI 90 response at Week 52 for patients with PASI 90 response at Week 24	Х	Х	Х			
PASI 90 response at Week 52 for patients with PASI 75 response but without PASI 90 response at Week 24	X	Х	Х			
PASI 50/75/90/100 response from Week 28 to Week 52 (or Week 60)	X	X				
IGA mod 2011 0 or 1 response from Week 28 to Week 52 (or Week 60)	Х	Х				
Time course of PASI from Week 24 to Week 52 and change of PASI compared to baseline				X	Х	
Time course of DLQI from Week 24 to Week 52 and change of DLQI compared to baseline				Х	Х	
Time course of DLQI 0 or 1 from Week 24 to Week 52	Х	Х				
Time course of EQ-5D-5L from Week 24 to Week 52 and change of EQ-5D-5L compared to baseline	Х			X	Х	
Time course of WPAI-PSO from Week 24 to Week 52 and change of WPAI-PSO compared to baseline				X	Х	
Time course of assessment of pain itching and scaling from Week 24 to Week 52 and change of this assessment compared to baseline				X	X	
PASI 50, 75, 90 and 100 response at Week 24	Х					
IGA mod 2011 0 or 1 response at Week 24	Х					
Time to PASI 90 response from Week 24 on for patients with PASI 75 response but without PASI 90 response at Week 24						X
Time to loss of PASI 75 response from Week 24 on for patients with PASI 75 response but without PASI 90 response at Week 24						Х
PK data and PASI response during course of the study						
Time to loss of PASI 90						Х

Variable(s)	Summary statistics for binary/ categorical	Risk Difference	Logistic regression	Summary statistics for continuous	Analysis of Co- variance	Time to event data analysis
	data			data		
response after Week 24 for patients with PASI 90 response at Week 24						
Time to loss of IGA mod 2011 0/1 response after Week 24						Х
Body Surface Area affected by plaque-type psoriasis at Week 52 and change from baseline				Х		
Time course of PASI from Baseline to Week 24 and change of PASI compared to baseline				Х		
PASI 50/75/90/100 response from Week 1 to Week 20	X					
IGA mod 2011 0 or 1 response from Week 1 to Week 20	X					
Time course of DLQI from Baseline to Week 24 and change of DLQI compared to baseline				Х		
Time course of EQ-5D-5L Baseline to Week 24 and change of EQ-5D-5L compared to baseline				X		
Time course of WPAI-PSO from Baseline to Week 24 and change of WPAI-PSO compared to baseline				Х		
Time course of assessment of pain itching and scaling from Baseline to Week 24 and change of this assessment compared to baseline				Х		
Relapse at Week 60	Х	Х				
Rebound at Week 60	Х	Х				

#### 1.8.1.1 Definition of total body surface area, PASI and related variables

The total body surface area (BSA) affected by plaque-type psoriasis is estimated from the percentages of areas affected, including head, trunk, upper limbs and lower limbs (see below for full details of the PASI assessment). The following calculations will be done: Each reported percentage will be multiplied by its respective body region corresponding factor (head = 0.1, trunk = 0.3, upper limbs = 0.2, lower limbs = 0.4). The resulting 4 percentages will be added up to estimate the total BSA affected by chronic plaque psoriasis.

The PASI in Treatment Period 2 is assessed by a blinded PASI assessor without access to the randomization details. It is recommended that the same person performs all PASI assessments for a single patient.

A PASI score (Fredriksson and Pettersson 1978, Weisman et al 2003, Gottlieb et al 2005) was derived as indicated in Table 1-8. The head, trunk, upper limbs and lower limbs are assessed separately for erythema, thickening (plaque elevation, induration), and scaling (desquamation). The average degree of severity of each sign in each of the four body regions is assigned a score of 0-4. The area covered by lesions on each body region is estimated as a percentage of the total area of that particular body region. Further practical details help the assessment:

- 1. The neck is assessed as part of the head.
- 2. The axillae and groin are assessed as part of the trunk.
- 3. The buttocks are assessed as part of the lower limbs.
- 4. When scoring the severity of erythema, scales should not be removed.

Because the head and neck, upper limbs, trunk and lower limbs correspond to approximately 10%, 20%, 30% and 40% of the body surface area, respectively, the PASI score was calculated using the formula:

$$PASI = 0.1 (E_h + I_h + D_h)A_h + 0.2 (E_u + I_u + D_u)A_u + 0.3 (E_t + I_t + D_t)A_t + 0.4 (E_l + I_l + D_l)A_l$$

where E, I, D, and A denote erythema, induration, desquamation, and area, respectively, and h, u, t, and l denote head, upper extremities, trunk, and lower extremities, respectively (see Table 1-8).

PASI scores can range from a lower value of 0, corresponding to no signs of psoriasis, up to a theoretic maximum of 72.0.

The PASI assessor was only responsible for collecting the components or scoring signs and total regional area and reported these data in a separate database. PASI calculations were done automatically within this system.

The PASI scores calculated via the PASI Score system will be used in the analysis and for derivation of PASI response values and relapse (see below).

Body region	Erythema (E)	Thickening (plaque elevation, induration, I)	Scaling (desquamation, D)	Area score (based on true area %, A)*
Head (H) †	0=none 1=slight 2=moderate 3=severe 4=very severe	0=none 1=slight 2=moderate 3=severe 4=very severe	0=none 1=slight 2=moderate 3=severe 4=very severe	0 = 0% 1 = 1-9% 2 = 10-29% 3 = 30-49% 4 = 50-69% 5 = 70-89% 6 = 90-100%
Trunk (T) ‡	0=none 1=slight 2=moderate 3=severe 4=very severe	0=none 1=slight 2=moderate 3=severe 4=very severe	0=none 1=slight 2=moderate 3=severe 4=very severe	0 = 0% 1 = 1-9% 2 = 10-29% 3 = 30-49% 4 = 50-69% 5 = 70-89% 6 = 90-100%
Upper limbs (U)	0=none 1=slight 2=moderate 3=severe 4=very severe	0=none 1=slight 2=moderate 3=severe 4=very severe	0=none 1=slight 2=moderate 3=severe 4=very severe	0 = 0% 1 = 1-9% 2 = 10-29% 3 = 30-49% 4 = 50-69% 5 = 70-89% 6 = 90-100%
Lower limbs (L) §	0=none 1=slight 2=moderate 3=severe 4=very severe	0=none 1=slight 2=moderate 3=severe 4=very severe	0=none 1=slight 2=moderate 3=severe 4=very severe	0 = 0% 1 = 1-9% 2 = 10-29% 3 = 30-49% 4 = 50-69% 5 = 70-89% 6 = 90-100%

\* Percentage (not score) of body region (not whole body) affected will be entered in the eCRF

The following definitions are based on the PASI and will be used for the efficacy evaluation in the current study:

- PASI 50 response: subjects achieving ≥ 50% improvement (reduction) in PASI score compared to baseline are defined as PASI 50 responders
- **PASI 75 response**: subjects achieving ≥ 75% improvement (reduction) in PASI score compared to baseline are defined as PASI 75 responders
- PASI 90 response: subjects achieving ≥ 90% improvement (reduction) in PASI score compared to baseline are defined as PASI 90 responders
- Maintaining of PASI 90 response at Week 52: maintaining of PASI 90 response at Week 52 is achieved for those subject from the FAS-P90R who achieved PASI 90 response as defined above at their Week 52 visit
- PASI 100 response: complete clearing of psoriasis (PASI=0)

<sup>† Neck is assessed as part of the Head (H) body region.

<sup>1 Axillae and groin are assessed as part of the Trunk (T) body region.

Buttocks are assessed as part of the Lower limbs (L) body region.

• **Relapse**: when the achieved maximum PASI improvement from baseline is reduced by > 50%, i.e. relapse is defined as the following condition being fulfilled:

$$1 - \frac{\cdot i}{D_{max,i}^+} > 0.5$$

where  $D_i$  is the difference in PASI between Baseline and Week i and  $D^+_{\max,i}$  is the maximum improvement in PASI between Baseline and any visit prior to Week i.

Rebound: A patient will be considered to have experienced a rebound, if the PASI increases to ≥125% of Baseline PASI, or if new pustular psoriasis, new erythrodermic psoriasis, or more inflammatory psoriasis occurs within 8 weeks after the last dose of study treatment has been received. For the current study rebound is assessed at the end of the Follow-Up period (i.e. Week 60 in the visit window described in Section 1.4.4).

#### 1.8.1.2 Definition of IGA mod 2011 score and IGA mod 2011 0 or 1 response

The IGA mod 2011 rating scale for overall psoriatic disease (shown in Table 1-9) has been developed based on a previous version of the scale used in AIN457 phase II studies, and has been updated in collaboration with health authorities. The explanations/descriptions of the points on the scale have been improved to ensure appropriate differentiation between the points.

The IGA mod 2011 used in this study is static, i.e., it refers exclusively to the subject's disease state at the time of the assessments, and does not attempt a comparison with any of the subject's previous disease states, whether at baseline or at a previous visit.

Table 1-9 The IGA mod 2011 rating scale

Score	Short Description	Detailed Description
0	Clear	No signs of psoriasis. Post-inflammatory hyperpigmentation may be present.
1	Almost clear	Normal to pink coloration of lesions; no thickening; no to minimal focal scaling.
2	Mild	Pink to light red coloration; just detectable to mild thickening; predominantly fine scaling.
3	Moderate	Dull bright red, clearly distinguishable erythema; clearly distinguishable to moderate thickening; moderate scaling.
4	Severe	Bright to deep dark red coloration; severe thickening with hard edges; severe / coarse scaling covering almost all or all lesions.

Note: Involvement of nails is not part of the assessment.

Based on this scale, subjects will be considered as IGA mod 2011 0 or 1 responder if they achieve a score of 0 or 1 and improve by at least 2 points on the IGA scale compared to baseline.

#### 1.8.1.3 Health-related Quality of Life

The impact of psoriasis on various aspects of patients quality of life (HRQoL) was assessed by the following validated patient reported outcomes (PROs):

Dermatology Life Quality Index (DLQI©)

- Patient's assessment of pain, itching and scaling
- European Quality of Life 5 Dimensions (EQ-5D)
- Work Productivity and Activity Impairment Questionnaire Psoriasis (WPAI-PSO)

#### Dermatology Life Quality Index (DLQI)

The DLQI measures functional disability of subjects with dermatological disorders that are greater than 18 years of age and had been utilized as a relevant clinical measure in atopic dermatitis, as well as other dermatitis clinical trials. The DLQI is a simple, validated, self-administered 10-item questionnaire. The instrument contains six functional scales (i.e., symptoms and feeling, daily activities, leisure, work and school, personal relationships, treatment). For the DLQI, each question will be answered with the following response: "not at all", "a little", "a lot", or "very much". "Not relevant" is also a valid response. Seven scores will be derived from the DLQI: the total score of each of the six dimensions as well as the total score over all items. The higher the score, the more quality of life is impaired.

#### Patients assessment of pain, itching and scaling

Self-administered, 11-point numeric rating scales (NRS, 0-10) are used to evaluate the patient's assessment of their current pain, itching and scaling. Respondents answer the following questions for the assessment of:

- Pain: Overall, how severe was your psoriasis-related pain over the past 24 hours?
- **Itching**: Overall, how severe was your psoriasis-related itch over the past 24 hours?
- Scaling: Overall, how severe was your psoriasis-related scaling over the past 24 hours?

Patients have to rate their pain, itching, and scaling from 0 to 10 (11-point scale), with the understanding that the 0 represents the absence or null end of the pain, itching, or scale intensity (i.e., no pain, itching or scaling) and the 10 represents the other extreme of pain, itching, or scaling intensity (i.e., pain, itching or scaling as bad as it could be). The number that the patient selects represents his or her intensity score in the respective category.

#### European Quality of Live - 5 Dimensions (EQ-5D)

The EQ-5D is a non-disease specific, validated and widespread instrument for quantifying life quality of patients. The EQ-5D quantifies the health state of a patient for the following five dimensions: Mobility, self-care, usual activities, pain/discomfort and anxiety/depression. In the current study the EQ-5D-5L version has been used which evaluates each of these dimensions using the following five labels: "no problems", "slight problems", "moderate problems", "severe problems" and "unable to/extreme problems".

Based on the five dimensions, a summary score (utility index) is derived using country specific value sets evaluating the patient condition described by the outcome in the single dimensions.

For the current analysis the EQ-5D-5L utility index based on the crosswalk value sets available from the EuroQol for Germany and for UK (http://www.euroqol.org/about-eq-5d/valuation-of-eq-5d/eq-5d-5l-value-sets.html) will be calculated and presented separately.

Additionally, a visual analogue scale (VAS) is used within the EQ-5D. This scale records the respondent's self-rated health on a vertical 20-cm VAS where the endpoints are labeled "best imaginable health state "and "worst imaginable health state." This results in a numeric value set ranging from 0 (="worst imaginable health state") up to 100 (="best imaginable health state").

# Work Productivity and Activity Impairment Questionnaire Psoriasis (WPAI-PSO)

The WPAI-PSO is a self-administered questionnaire comprising of six questions about effects of psoriasis on the patient's ability to work and perform regular activities based on their experiences in the previous 7 days. The questionnaire quantifies the number of hours that the respondent was unable to work and, using a 10-point scale, evaluates the extent to which the respondent's psoriasis affected their productivity while working. For respondents who are not in paid employment, the questionnaire evaluates the extent to which the respondent's psoriasis affects their ability to perform regular daily activities.

The WPAI-PSO consists of six questions:

- Q1 = currently employed
- Q2 = hours missed due to health problems
- Q3 = hours missed due to other reasons
- Q4 = hours actually worked
- Q5 =degree health affected productivity while working
- Q6 = degree health affected productivity in regular unpaid activities.

The recall period for the questions 2 to 6 is seven days. Four main outcomes can be generated from the WPAI-PSO and expressed in percentages:

- % Absenteeism: percent work time missed due to health for those who were currently employed (i.e., only patients with Q1=Yes)
- % Presenteism: percent impairment while working due to health for those who were currently employed and actually worked in the past seven days (i.e., only patients with O1=Yes)
- % Total work productivity impairment: percent overall work impairment due to health for those who were currently employed (i.e., only patients with Q1=Yes)
- % Total activity impairment: percent activity impairment due to health for all respondents

The percentage of impairment while working (presenteism) is calculated as Q5/10 x 100%. The percentage of work time missed (absenteeism) is calculated as Q2/(Q2 + Q4) x 100%. The percentage of total work productivity impairment (i.e., work productivity loss) is  $(Q2/(Q2 + Q4) + (1-Q2/(Q2+Q4)) \times (Q5/10)) \times 100\%$ . The percentage of total activity impairment is

calculated as Q6/10 x 100%. In case of missing items the respective outcomes where these items are utilized cannot be calculated.

#### 1.8.2 Statistical hypothesis, model, and method of analysis

The statistical null-hypothesis to be rejected in the primary analysis is that the odds ratio of maintaining a PASI 90 response for patients with secukinumab 4-weekly dosing versus patients on secukinumab 6-weekly dosing exceeds the non-inferiority margin of  $1+\delta$ .

The primary hypothesis is stated as follows:

Let  $\pi_j$  denote the probability of a PASI 90 response at Week 52 for dosing group j, j=0, 1, where

- 0 corresponds to 4-weekly dosing
- 1 corresponds to 6-weekly dosing

The following hypothesis will be tested

$$H_{01}$$
:  $(\pi_0 / (1 - \pi_0)) / (\pi_1 / (1 - \pi_1)) \ge 1 + \delta$  versus  $H_{A1}$ :  $(\pi_0 / (1 - \pi_0)) / (\pi_1 / (1 - \pi_1)) < 1 + \delta$ 

The non-inferiority margin  $1+\delta$  is calculated as 2.23 assuming a PASI 90 response maintenance rate of 81.8% under 4-weekly dosing treatment scheme and using a 15% non-inferiority margin. The **primary analyses** will be performed comparing dosing groups (Group 1 vs. Group 2) with respect to the primary efficacy variable in a logistic regression model with the factors dosing group, country, PASI 90 response at Week 16 (Yes, No) and body weight at Week 24 (< 90 kg or  $\geq$  90 kg, for model definition see Section 2.2.2). The odds ratios and their two-sided 95%-Wald confidence intervals (CIs) will be given.

In case of subgroup analyses where the grouping variable is one of the above described factors in the logistic regression model the respective factor is excluded from the model.

Additionally, the one-sided p-value for the shifted null-hypothesis will be given. The respective test statistic is calculated as

$$\frac{\hat{\beta}-\beta_0}{se_{\hat{\beta}}}$$

where  $\hat{\beta}$  is the type 3 maximum likelihood estimate of the dosing group parameter in the logistic regression model and  $se_{\hat{\beta}}$  is its standard error.  $\beta_0$  is the non-inferiority margin of the estimator which corresponds to the  $\delta$  from the above null-hypothesis and is therefore set to  $ln(1+\delta) = ln(2.23) = 0.80$ .

Only in case that the number of patients with response (or non-response) in one of the groups is 5 or lower, exact logistic regression will be used for the primary analysis instead of logistic regression using maximum-likelihood based estimators.

The primary analysis set will be the FAS-P90R.

#### 1.8.3 Handling of missing values/discontinuations

Patients who drop out prematurely and/or do not have a valid PASI assessment at Week 52 will be counted as non-responders. Patients with major protocol violations, but with a valid PASI assessment will be included in the intention-to-treat (ITT)-analysis (i.e. primary analysis) with their observed response. The same algorithm will be used for the key secondary endpoint, the PASI 90 response at Week 52 in the FAS-P75R set. Missing values for secondary endpoints or other outcomes (e.g. quality of life, safety or lab measurements) will not be replaced.

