#### 1.8 Efficacy evaluation

#### 1.8.1 Variables

The primary efficacy variable is the maintaining of PASI 90 response at Week 52 for patients with PASI 90 response at Week 24. The primary analysis of this primary variable will be based on the FAS-P90R.

Table 1-5 lists the primary, key secondary, secondary and exploratory variables for this study. The testing strategy for the analysis of the primary variable is described in Section 1.8.6.

\*: number of treatment (e.g. two treatment cycles with the same medication are counted twice)

\*\*: at least one therapy with lack of efficacy or lack of tolerability

Table 1-5 Primary, key secondary, secondary and exploratory efficacy variables as described in the protocol by treatment period

Variable	Туре	Treatment Period
PASI 90 response at Week 52 for patients with PASI 90 response at Week 24	primary	TP2
PASI 90 response at Week 52 for patients with PASI 75 response but without PASI 90 response at Week 24	key secondary	TP2
PASI 50/75/100 response at Week 52	secondary	TP2
IGA mod 2011 0 or 1 response at Week 52	secondary	TP2
Time course of PASI from Week 24 to Week 52 and change of PASI compared to baseline 	secondary	TP2/FU 
Time course of DLQI from Week 24 to Week 52 and change of DLQI compared to baseline	secondary	TP2
Time course of DLQI 0 or 1 from Week 24 to Week 52	secondary	TP2
Time course of EQ-5D-5L from Week 24 to Week 52 and change of EQ-5D-5L compared to baseline	secondary	TP2
Time course of WPAI-PSO from Week 24 to Week 52 and change of WPAI-PSO compared to baseline	secondary	TP2
Time course of assessment of pain itching and scaling from Week 24 to Week 52 and change of this assessment compared to baseline	secondary	TP2
PASI 50, 75, 90 and 100 response at Week 24	exploratory	TP1
IGA mod 2011 0 or 1 response at Week 24	exploratory	TP1
Time to PASI 90 response from Week 24 on for patients with PASI 75 response but without PASI 90 response at Week 24	exploratory	TP2
Time to loss of PASI 75 response from Week 24 on for patients with PASI 75 response but without PASI 90 response at Week 24	exploratory	TP2
PK data and PASI response during course of the study	exploratory	TP1/TP2
Time to loss of PASI 90 response after Week 24 for patients with PASI 90 response at Week 24	exploratory	TP2
Time to loss of IGA mod 2011 0/1 response after Week 24	exploratory	TP2

1: for patients in the FAS-P75R also the Week 60 visit will be considered for this analysis

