
Additional efficacy endpoints not described in the protocol but included in the analysis are listed in Table 1-6.

Table 1-6 Additional efficacy variables not described in the protocol by treatment period

Variable	Туре	Treatment Period
PASI 50/75/90/100 response from Week 24 to Week 48 	additional secondary	TP2/FU 
IGA mod 2011 0 or 1 response from Week 24 to Week 48 	additional secondary	TP2/FU 
Body Surface Area affected by plaque-type psoriasis at Week 52 and change from baseline	additional exploratory	TP2
Time course of PASI from Baseline to Week 24 and change of PASI compared to baseline	additional exploratory	TP1
PASI 50/75/90/100 response from Week 1 to Week 20	additional exploratory	TP1
IGA mod 2011 0 or 1 response from Week 1 to Week 20	additional exploratory	TP1
Time course of DLQI from Baseline to Week 24 and change of DLQI compared to baseline	additional exploratory	TP1
Time course of EQ-5D-5L Baseline to Week 24 and change of EQ-5D-5L compared to baseline	additional exploratory	TP1
Time course of WPAI-PSO from Baseline to Week 24 and change of WPAI-PSO compared to baseline	additional exploratory	TP1
Time course of assessment of pain, itching and scaling from Baseline to Week 24 and change of this assessment compared to baseline	additional exploratory	TP1
Relapse at Week 60	additional exploratory	FU
Rebound at Week 60	additional exploratory	FU

1: the analysis of this variable will be added to the respective analysis for Week 52

An overview of statistical analyses and methods applied to efficacy variables is given in Table 1-7

2: for patients in the FAS-P75R also the Week 60 visit will be considered for this analysis

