# PASI 50/75/90/100 and IGA mod 2011 0 or 1 response over time in Treatment Period 2 and Follow-Up Period

Summary statistics for PASI 50/75/90/100 response and for IGA mod 2011 0 or 1 response from Week 24 to Week 52 will be presented for the FAS-P90R and the FAS-P75R separately in contingency tables including absolute and relative frequencies. For the FAS-P75R also the response rates at Week 60 will be provided. Risk differences between the dosing groups will also be provided.

Figures will be provided as well displaying estimates for responder rates by dosing group.

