#### 2.2.3 Multiple imputations for response variables

Non-responder imputation as primary analysis will be performed since low drop-out rates are expected. It is expected that subjects will be likely to drop-out due to lack of efficacy, such that a non-responder imputation will be reasonable.

In the multiple imputations analysis the response status will be imputed based on the individual treatment arm information.

Multiple imputation (MI) is a simulation based approach where missing values are replaced by multiple Bayesian draws from the conditional distribution of missing data given the observed data and covariates, creating multiple completed data sets. These completed data sets can then be analyzed using standard methods. Rubin (1987) presented rules how to combine the multiple sets of estimates to produce overall estimates and confidence intervals that adequately incorporate missing data uncertainty.

Missing values for the 'change from baseline PASI score' will be imputed based on an underlying joint normal distribution and using a Markov Chain Monte Carlo (MCMC) method. The change from baseline in PASI score appears to follow closer to a normal distribution than the actual PASI score.

Page 41

The imputations will be done separately for each dosing group including weight at Week 24 (in groups) as additional covariate. Values post assessment timepoint of the primary endpoint will not be considered for imputations.

The number of imputations will be set to 50, the seed for the random function will be set to 4573302 for this study. To generate the multiple imputed data sets, the SAS procedure MI can be used as follows:

The input data set <pasi> should have one record per subject with baseline PASI score as well as all changes from baseline PASI starting with Week 28.

```
ODS LISTING CLOSE;
ODS OUTPUT MissPattern=miinfo_msgpat VarianceInfo=varinfo ParameterEstimates=param;
PROC MI DATA=<pasi> OUT=<impdata> SEED=4573302 NIMPUTE=50;
 VAR <weight at Week 24> >
     <baseline PASI>
     <change from baseline PASI week 24> - <change from baseline PASI week primary endpoint>;
RUN;
ODS LISTING;
```

Two outputs will be prepared displaying i) the missing data patterns and the group means as stored in the data set msgpat and ii) the variance information and estimated means with confidence interval and range based on data sets varinfo and param which need to be merged by <dosing group>.

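### Non-responder imputation covers only PASI 90 at Week 52; the other Treatment Period 2 responder rates are not replaced and have no stated denominator

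*SAP*

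**What the plan says.** - **Missing data.** SAP 1.8.3 treats a missing Week 52 PASI 90 as non-response in FAS-P90R (primary) and in FAS-P75R (key secondary). It continues: "Missing values for secondary endpoints or other outcomes (e.g. quality of life, safety or lab measurements) will not be replaced". Protocol 9.4.4 sets the same limit. Multiple imputation (SAP 1.8.4(C) and 2.2.3) also covers only Week 52 PASI 90.
- **Reason given for the rule.** SAP 2.2.3: "Non-responder imputation as primary analysis will be performed since low drop-out rates are expected", followed by "It is expected that subjects will be likely to drop-out due to lack of efficacy, such that a non-responder imputation will be reasonable".
- **Status of the other responder endpoints.** SAP Table 1-5 lists "PASI 50/75/100 response at Week 52" as secondary, and also IGA 0/1 at Week 52 and DLQI 0/1 over time. Table 1-6 lists "PASI 50/75/90/100 response from Week 24 to Week 48", and IGA 0/1 over the same visits, as additional secondary. Its footnote 1 says that "the analysis of this variable will be added to the respective analysis for Week 52".
- **Display.** SAP 1.8.7 tabulates PASI and IGA response by visit through Week 52 in each full analysis set, and also at Week 60 in FAS-P75R. "Risk differences between the dosing groups will also be provided", and "Figures will be provided as well displaying estimates for responder rates by dosing group". The section gives no missing-data rule and no denominator.
- **Method table.** SAP Table 1-7 has one row each for the primary and key secondary variables. A separate by-visit row for PASI 50/75/90/100 includes Week 52.
- **Subgroups.** SAP Table 1-2 plans Week 52 PASI 50/75/90/100 for all nine subgroup variables.

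**The concern.** The SAP's reason for non-responder imputation is that patients tend to leave because the drug is not working well enough. That reason applies equally to PASI 75 at Week 52 or PASI 90 at Week 48, yet those rates are not replaced. If patients without a value fall out of the denominator, the remaining patients are a favourable selection and the rate is too high. If more patients leave one group than the other, the risk difference moves as well.

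The rates are also nested: every PASI 90 responder is a PASI 75 responder. At Week 52, PASI 90 would count leavers as failures while PASI 75 and PASI 100 would omit them, so part of the gap between the thresholds would come from the rule. At stake is the reading of the secondary rates, risk differences, figures and subgroup tables.

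**Working it through.** **1. Check of the planning rates.** SAP 1.11 and Protocol 9.7 assume maintenance rates of 81.8% (4-weekly) and 74.8% (6-weekly), a 15-point margin, one-sided 2.5% and 90% power, giving 554 per group.

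n = (1.960 + 1.282)² × (0.818 × 0.182 + 0.748 × 0.252) / (0.15 − 0.07)² = 10.507 × 0.3374 / 0.0064 = 553.9, so 554. The figure is reproduced. Both documents say these rates come from data analysed with the same drop-out algorithm, so they are rates with leavers counted as failures.

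**2. Effect of leaving patients out.** Let m be the share without a value.

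Observed-case rate = rate with leavers as failures / (1 − m).

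The multiplier is 1.01 at m = 1%, 1.02 at 2%, 1.05 at 5% and 1.11 at 10%. The documents call drop-out low and give no percentage, so every m here is an assumption.

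**3. PASI 90 in FAS-P90R.** This assumes that the planning rates hold at both Week 48 and Week 52 and that all drop-out comes before Week 48.

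| Assumed drop-out, 4-weekly/6-weekly | Observed-case, 4-weekly | Observed-case, 6-weekly | Excess over 81.8 and 74.8 | Group difference (7.0 with leavers as failures) |
|---|---|---|---|---|
| 1%/2% | 0.818/0.99 = 82.6% | 0.748/0.98 = 76.3% | 0.8 and 1.5 | 6.3 |
| 5%/5% | 0.818/0.95 = 86.1% | 0.748/0.95 = 78.7% | 4.3 and 3.9 | 7.4 |
| 5%/10% | 0.818/0.95 = 86.1% | 0.748/0.90 = 83.1% | 4.3 and 8.3 | 3.0 |

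**4. Nested rates at Week 52.** Take the 4-weekly group at 5% drop-out. PASI 90 is reported as 81.8%. Observed-case PASI 75 cannot be below observed-case PASI 90, which is 86.1%. A gap of at least 4.3 points between PASI 75 and PASI 90 would appear even if no patient lay between the two thresholds.

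**5. PASI 90 in FAS-P75R.** The planned rates are low (Protocol 9.7.1: 3.8% on 4-weekly, 18% on 2-weekly dosing), so the effect is small. At 2%, 5% and 10% drop-out the excess is 0.4, 0.9 and 2.0 points on 18%, and 0.1, 0.2 and 0.4 points on 3.8%.

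**6. The PASI 90 course.** Two readings are open.
- *Switch of basis.* Table 1-6 footnote 1 joins the unreplaced Week 24 to 48 rates to the Week 52 analysis, which 1.8.3 makes non-responder imputed. The excess in step 3 then appears as a fall from Week 48 to Week 52 with no change in any patient's skin.
- *Observed cases throughout.* The by-visit row in Table 1-7 is separate from the primary row and stands among the secondary analyses. If it follows the secondary-endpoint sentence in 1.8.3, the curve has no step. The same excess is then the gap between two reported Week 52 PASI 90 rates.

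**The case against.** - **The choice is prespecified and consistent.** Protocol 9.4.4 and SAP 1.8.3 agree. A reader might infer a contradiction between the documents, but there is none. This stands; the point is about the merit of the choice.
- **The step at Week 52 is not established.** A reader might infer that the PASI 90 curve certainly changes basis after Week 48. Table 1-7's by-visit row allows the other reading, and Table 1-6 footnote 1 says only that the analyses are presented together. This stands. Either reading still leaves something to correct.
- **The denominator is not written.** With the full analysis set as denominator, a missing value would already count as non-response. This stands as a limit. Omission is the likelier reading of values that are not replaced, and the SAP should say which applies.
- **Other analyses deal with drop-out.** Table 2-1 has an informative-censoring entry for discontinuation due to lack of efficacy in the time-to-loss analyses. Reasons for discontinuation are tabulated (SAP 1.5.1). Under Protocol 5.5.10, patients who stop drug still have end-of-treatment assessments. These help interpretation but do not put the responder rates on one basis, and an early end-of-treatment assessment does not supply values at all later visits.
- **The effect may be trivial.** At 1%/2% the difference moves by 0.7 points. The unadjusted 95% half-width at 570 per group is 1.96 × √(0.3374/570) = 4.8 points. This stands if drop-out is as low as the SAP expects. The 3.0-point result needs 10% drop-out in one group, for which the documents give no support.

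**Conclusion.** The concern holds for the secondary responder rates. The plan leaves PASI 50/75/100 and IGA 0/1 at Treatment Period 2 visits, PASI 90 before Week 52, and DLQI 0/1 unreplaced, although its own argument for counting leavers as failures applies to them too. On the likely reading of the denominator, the rates can be inflated by a factor 1/(1 − drop-out), and risk differences shift if drop-out differs by group. A PASI 90 difference of 7.0 points would show as 6.3 at 1%/2% and as 3.0 at 5%/10%. These figures rest on assumed drop-out, on the planning rates holding at the visit shown, and on leavers being omitted. At Week 52, PASI 75 and PASI 100 are then not comparable with PASI 90.

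The PASI 90 course is ambiguous: the text supports either a switch of basis at Week 52 or a second Week 52 rate that differs from the primary one, and does not decide between them. A reader might also infer that the non-inferiority or superiority conclusion is at risk. It is not: both confirmatory endpoints have an explicit rule, and their tests, significance levels and sample size are untouched.

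**What to change.** In SAP 1.8.3:
1. Count patients without a valid assessment as non-responders, with the analysis set as denominator, for PASI 50/75/90/100 and IGA 0/1 at every Treatment Period 2 visit and for DLQI 0/1 at its scheduled visits.
2. State that Week 52 PASI 90 follows this rule in every table, figure and subgroup.
3. For Week 60 in FAS-P75R, either use the same rule or label the change of basis. Otherwise the break only moves from Week 52 to Week 60.
4. Where a window is empty only because an attended visit was re-mapped by study day (SAP 1.4.4), use that visit's assessment and do not score non-response.
5. Show observed-case rates, with denominators, as supportive.
6. Leave continuous endpoints as they are.

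List the departure from Protocol 9.4.4 in SAP 1.1.1.

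The cost is SAP wording, one line in 1.1.1, re-use of the existing derivation and the handling of re-mapped visits. The downside is that displayed rates will be slightly lower and an isolated missed visit counts as non-response even between two responding visits. The observed-case display is kept for that reason.
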